13.2.3. Analysis of Safety Data

All safety data will be analysed on the safety population. Prior to analysis, adverse drug reactions will be coded using MedDRA.

Incidence and characteristic of adverse drug reactions will be described and presented in summary tables using absolute frequencies and percentages as well as 95% confidence intervals;

Evaluation of AEs, including the AEs, will consist of the determination of total number of AEs, total number of patients with AEs and the number of AEs requiring discontinuation of the study treatment. The incidence and severity of all AEs will be summarized by body system. Treatment discontinuation due to AEs will be tabulated

AEs reported in the study as well as AEs reported directly to authorities and to Takeda International Drug Safety according to section 11.3 and not captured in the study database will be extracted from the overall safety database and the study database and listed or tabulated in the final report in the standard way of presenting such data in a Periodic Safety Update Report (PSUR).

13.2.4. Potential study biases

The study limitations are those inherent to uncontrolled observational studies. Taking into account observational and uncontrolled nature of the study, fully evaluating of azilsartan medoxomil efficacy will not be available. However data regarding blood pressure (SBP and DBP) dynamic during and after azilsartan medoxomil titration in real-life practice will be gathered and analyzed. The inclusion criteria are those that used when administering azilsartan medoxomil in practice and therefore, the same criteria as those that would have been used if we had performed a similar prospective study. This type of experimental design should prevent selection bias that could occur when patient enrollment is related to the development of the outcome. In prospective observational study like this attrition bias is possible, however, in case of early leaving study last BP data will be gathered and efficacy will be estimated, these cases will not be excluded from efficacy analysis.

Details of the statistical analyses will be presented in the Statistical Analysis Plan.

13.2.5. Data handling

13.2.5.1. Missing data and invalid data

Missing data will not be restored. No procedures for missing data pattern assessment and/or imputation are planned. Outlier detection will be performed during blind data review, using modified Z-score([32] calculation

$$M_i = \frac{0.6745(x_i - \tilde{x})}{\text{MAD}},$$

with MAD denoting the median absolute deviation and \tilde{x} denoting the median.

Values of modified Z-score >3.5 will be considered outliers for univariate data sets that are assumed to follow an approximately normal distribution. If the normality assumption for the data being tested is not valid, then a determination of outlier using interquartile range and median (values more than 1.5 times the interquartile range will be considered outliers). Outliers will not be excluded from primary analysis *en bloc*, however, the medical context for each outlier will be defined and appropriate action taken. List of outliers flagged and actions taken will be included into Statistical Analysis Report. An additional sensitivity analysis will be performed excluding outliers.

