A snapshot of the clinical database will be generated after all subjects have completed through the final visit of the study or discontinued participation in the study. Snapshot for final analysis will be performed after database lock according to relevant CRO's Standard Operating Procedure (SOP) for database lock and data extraction. All tables, figures, and listings (TFLs) described in this SAP will be generated on this snapshot of the database.

Database for interim analysis

As soon as first 470 study patients have completed through final visit of the study or discontinue their participation a snapshot of the clinical database will be generated. The snapshot of the database will be performed in accordance with Standard operating procedures of CRO responsible for Data collection and data management. All tables, figures and listings described in this SAP will be generated on this interim snapshot of the database

Database for final analysis in the Republic of Kazakhstan

Analysis, according to this particular Statistical Analysis Plan, will be performed only for the data obtained in the Republic of Kazakhstan.

A snapshot of the clinical database will be generated after all patients have completed through the final visit of the study or discontinued participation in the study. Snapshot for final analysis will be performed after database lock according to relevant CRO's Standard Operating Procedure (SOP) for database lock and data extraction. Statandocs will receive the data related to study participants from Republic of Kazakhstan only, via the agreed communication channels.

All tables, figures, and listings (TFLs) described in this SAP will be generated on this snapshot of the database (with data from Republic of Kazakhstan only).

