where MAD – median absolute deviation, x - median.

Values with Z-score > 3.5 will be considered outliers for study variables considered normally distributed. Preliminary normality test (Shapiro–Wilk criterion) will be performed for these variables. In case if normality distribution hypothesis will be rejected based on Shapiro–Wilk test results, median and IQR (interquartile range) will be used for outlier identification. Values > 1.5 IQR far from median value will be considered outliers. No data will be excluded / modified based on outlier identification, however, additional medical context assessment for these data will be performed and data quality control / source verification check will be considered.

Data Monitoring

Data quality monitoring, including safety data review and reconciliation, will be implemented periodically by the Data Manager from a Contract Research Organization (CRO). Details will be described in the Data Management Plan.

Multiple Comparisons/Multiplicity

When needed, corrections for multiplicity will be justified and performed according to Bonferroni. Overall alpha-level will be controlled and will not exceed 0.05

The interim analysis will not be taken into account within multiplicity adjustment procedure.

Examination of Subgroups

Primary and some secondary and exploratory endpoints will be analyzed in subgroups of patients: overweight, obese (stages I-III), impaired glucose tolerance (yes, no), metabolic syndrome (yes, no), diabetes mellitus (yes, no) etc (see "EFFICACY ANALYSES" chapter).

This analysis may be limited for the Republic of Kazakhstan sample as this sample has limited sample size. This will be noted in the statistical analysis report accordingly.

6. STUDY POPULATION CHARACTERISTICS Patient Disposition

Data regarding how many patients reached the various stages of the trial, how many dropped out, discontinued the treatment and for what reasons (death, ADRs, treatment failure, withdrew consent, lost to follow-up) will be presented for each subgroup and for study in bulk. Standard diagram describing study patient flow will be provided.

7. DEMOGRAPHICS AND OTHER BASELINE CHARACTERISTICS Demographics

All demographic and other Baseline characteristics will be summarized for overall analysis population as well as for subgroups of patients listed in the section 9.3 of the document

Medical History, Concurrent Medical Conditions and comorbidities

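### If the non-normal outlier branch is used, its fence of 1.5 IQR from the median flags about 4% of ordinary normal-shaped data, and the Protocol's outlier-excluded sensitivity interval comes out about 10% too narrow

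*Protocol*

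**What the plan says.** Protocol section 13.2.5.1 has two branches. For roughly normal data: "Values of modified Z-score >3.5 will be considered outliers for univariate data sets that are assumed to follow an approximately normal distribution". Otherwise it prescribes "a determination of outlier using interquartile range and median (values more than 1.5 times the interquartile range will be considered outliers". It names the median but does not spell out the point from which the distance is measured.

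SAP section 5 (Outlier identification) does spell it out: "Values > 1.5 IQR far from median value will be considered outliers". It also sets the switch between branches: "In case if normality distribution hypothesis will be rejected based on Shapiro–Wilk test results", the IQR rule applies. The level of that test is not given.

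The documents differ on what happens to flagged values. In the Protocol, "Outliers will not be excluded from primary analysis" as a block; each is reviewed in its medical context and acted on, and then "An additional sensitivity analysis will be performed excluding outliers". The SAP says "No data will be excluded / modified based on outlier identification", has no analysis without outliers, and uses a flag only to prompt medical review and a possible source check. SAP section 4 limits its own reach: "Analysis, according to this particular Statistical Analysis Plan, will be performed only for the data obtained in the Republic of Kazakhstan".

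**The concern.** The familiar fence lies 1.5 IQR beyond the quartiles. Measured from the median, the same multiple falls well inside the range of ordinary values, so the rule cannot separate errors from normal tails. The two branches of one rule also differ greatly in strictness for data of the same shape.

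At stake is the Protocol's sensitivity analysis, which is meant to show that the systolic blood pressure (SBP) result does not depend on a few odd values. If the flags come from this branch, the analysis removes real patients from the tails. It then reports a smaller SD and a tighter interval, which a reader could take as evidence of robustness. If the SAP's no-exclusion statement governs, the cost is only unnecessary checking.

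**Working it through.** **Inputs.** From Protocol section 13.4: SD 17.79, correlation 0.4375, half-width 1 mm Hg, probability 0.9, 1437 pairs, 25% dropout, 1916 enrolled. From Protocol section 13.2.5.1 and SAP section 5: the 1.5 IQR and 3.5 cut-offs. Assumed: Shapiro–Wilk at 0.05; the modified Z-score read in absolute value; a Kazakhstan sample of about 160 pairs (1437 × 10/90, by share of sites).

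**The plan's own figure.** SD of the paired difference = 17.79 × √(2 × (1 − 0.4375)) = 18.87. The exact conditional precision calculation gives 1437 pairs with probability 0.903, and 1437/0.75 = 1916. Both are reproduced. The documents give no flag rate for the outlier rule.

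**Flag rates on a normal benchmark.** IQR = 2 × 0.6745 = 1.349 SD. Flag rate p = 2 × (1 − Φ(c)).

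| Rule | Cut-off c (SD) | Flagged | Of 1437 |
|---|---|---|---|
| Median ± 1.5 IQR | 1.5 × 1.349 = 2.02 | 4.30% | 61.8 |
| Quartiles ± 1.5 IQR | 0.6745 + 2.0235 = 2.70 | 0.70% | 10.0 |
| Modified Z beyond ±3.5 | 3.50 | 0.047% | 0.7 |

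The plan's two branches therefore differ about 92-fold (4.30/0.047). Inside the IQR branch, the chance of at least one flag is 1 − (1 − 0.0430)^n: 0.999 at n = 160 and essentially 1 at n = 1437.

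**Effect of exclusion.** SD ratio after truncation = √(1 − 2cφ(c)/(1 − p)) = √(1 − 2 × 2.0235 × 0.0515/0.957) = 0.884. Interval width ratio = 0.884/√0.957 = 0.904. At n = 1437 the half-width falls from 0.976 to 0.883 mm Hg. With quartile fences the ratio is 0.975.

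Simulated coverage of the nominal 95% interval after exclusion is about 87–88% for clean normal data. Narrowing alone would leave about 92% (1.96 × 0.904 = 1.77); the rest is lost because the trimmed mean varies more between samples than the full mean.

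**Other shapes, simulated at n = 1437.**

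| Shape | Flagged, median fence | Interval narrower by | Mean shift (mm Hg) | Quartile fences, for comparison |
|---|---|---|---|---|
| t, 5 df | 8.2% | 24% | about 0 | 3.4% flagged, 16% narrower |
| Gamma, skewness 0.5 | 4.6% | 12% | −1.7 | 1.2% flagged, shift −0.7 |
| Uniform | 0% | 0% | 0 | not run |

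**How often the branch is reached.** Simulated Shapiro–Wilk rejection for SBP change, with normal underlying values:

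| Rounding of each reading | n = 1437 | n = 160 |
|---|---|---|
| None | about 5% | about 4–6% |
| 1 mm Hg | about 10% | about 4–6% |
| 2 mm Hg | about 45% | about 4–6% |
| 5 mm Hg | 100% | about 29% |
| 10 mm Hg | 100% | 100% |

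The n = 1437 column shows what would happen if the SAP's test were applied to the whole study; the Protocol does not prescribe that test.

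**The case against.** The strongest reply is that the harm joins two documents that do not connect. The Shapiro–Wilk switch is only in the SAP, which covers Kazakhstan alone and excludes nothing. Exclusion is only in the Protocol, which names no test and asks only whether approximate normality is tenable. This stands in part. Under the SAP, over-flagging costs checking time and cannot distort an interval. But the Protocol commits the full study to the exclusion analysis, and a Kazakhstan-only SAP does not withdraw it.

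Three stronger readings are tempting and are not supported:

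- *The rule always fires, even on clean data.* Clean normal data belong to the modified Z branch and enter the IQR branch only on a false rejection, about 5% of the time. A flag is near-certain only inside the branch, and only for normal or heavier tails; uniform data give none.
- *Rounded blood pressure makes the loose branch the default.* Neither document states the recording precision, and up to 2 mm Hg at n = 160 the rejection rate stays near nominal.
- *Laboratory means will be biased.* Nothing says that laboratory means will be re-estimated without outliers.

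It is also fair to say that the Protocol only implies the median as its anchor, that 10% is a normal benchmark for a branch meant for non-normal data, and that a half-width of 0.88 instead of 0.98 mm Hg around an assumed change of −17.3 mm Hg would not alter a conclusion on symmetric data.

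**Conclusion.** The point holds conditionally. When normality is judged not valid, the rule cuts at the median ± 1.5 IQR (explicit in the SAP, the natural reading of the Protocol). On a normal-shaped benchmark it flags about 4.3% of values, against 0.7% with quartile fences. If the Protocol's exclusion analysis then uses those flags, its interval is about 10% too narrow and covers about 87–88%. For the non-normal shapes tried, the narrowing ran from 0 to 24%, and moderate skew moved the mean by 1.7 mm Hg.

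How often this happens cannot be settled from the documents, because it depends on the variable's shape and on rounding. The 1437/1916 sample size is unaffected. So is the primary interval, since flagged values stay in as a group, although the Protocol leaves room for action on individual values. The matter should be corrected because the affected result is the one offered as evidence of robustness, and the correction costs almost nothing.

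**What to change.** 1. In Protocol section 13.2.5.1 and SAP section 5, define the non-normal branch as values below Q1 − 1.5 IQR or above Q3 + 1.5 IQR.
2. Limit the exclusion sensitivity analysis to flagged values that source verification could not confirm. Quartile fences alone do not suffice: in the skewed example, blanket exclusion still moved the mean by 0.7 mm Hg.
3. Reconcile the two documents: either carry that sensitivity analysis into the SAP, or remove it from the Protocol.

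The cost is a few words in each document and a small programming change. The downside is minor: fewer values are flagged for medical review.

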5. STATISTICAL / ANALYTICAL ISSUES

Visit windows

In accordance with the protocol, due to the non-interventional study design it's not possible to appoint exact times for the study visits, although it is expected that the period of observation will be approximately 6 months. The frequency of the visits will be assigned by each physician according to their routine practice. It is anticipated that the patients will visit their physician every 3 months and more often at the beginning until the patient achieves target blood pressure.

So, for the analysis and summary of clinical laboratory, efficacy, and safety data in case of this analysis/summary performed on "by visit" base. In the event of multiple values for an assessment within an analysis window, the value closest to the scheduled visit date will be used for analyses. If two values tie as closest to the time point (for example, one value is before and the other value is after the time point), then the later value will be selected as the analysis value.

Analysis Window	Start	End	Target Asses dupli	sment to be used if cates	
Baseline visi	t <1		NA		
Month 1 Month 3 Month 6	2 46 136	45 135 NA	30 90 Closes 180 equidi	st to target day, if stant use later result.	

The definition for the study days included in each study window is defined as below:

Treatment Day prior to first dose = Visit Date – Date of First Dose

Treatment Day on or after first dose = Visit Date – Date of First Dose + 1

Adjustments for Covariates

No specific adjustments for covariates will be made in all statistical analyses, unless specified otherwise per-analysis level.

Handling of Dropouts or Missing Data

Missing efficacy outcomes will be assumed to be missing at random (MAR) and thus will not be imputed in the primary analysis. However, if greater than 1% of all primary/secondary outcomes that should be available for analysis are missing, a sensitivity analysis will be undertaken in addition to the primary MAR analysis.

Confidential

This sensitivity analysis will include an evaluation of the results of models developed under the assumptions of:

1) last observation carried forward;

2) worst extreme case imputation and;

3) regression model imputation using all available information.

Outlier identification

During data Quality Control outlier identification will be performed using adjusted Z-score method (Iglewicz and Hoaglin, 1993).

$$M_i = \frac{0.6745(x_i - \tilde{x})}{MAD}$$

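### The fallback outlier limit, 1.5 IQR measured from the median, is only about 2 SD, so the protocol's outlier-excluded sensitivity analysis would drop genuine values and report too narrow an interval

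*Protocol*

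**What the plan says.** Protocol 13.2.5.1 sets a first-line rule for data taken to be approximately normal: "Values of modified Z-score >3.5 will be considered outliers for univariate data sets". Its fallback begins "If the normality assumption for the data being tested is not valid, then a determination of outlier using interquartile range and median", and the limit is "values more than 1.5 times the interquartile range will be considered outliers". Outliers are not removed wholesale from the primary analysis. Each is reviewed in its medical context and acted on as appropriate, and the flags and actions are listed in the report. The section then adds: "An additional sensitivity analysis will be performed excluding outliers".

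SAP section 5 (Outlier identification) places the same two rules within data quality control. It states the reference point outright, "Values > 1.5 IQR far from median value will be considered outliers", and names the switch: "Preliminary normality test (Shapiro–Wilk criterion) will be performed for these variables". On consequences it departs from the protocol: "No data will be excluded / modified based on outlier identification". SAP sections 2.4 and 4 confine this SAP's analysis to the data from the Republic of Kazakhstan.

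**The concern.** The familiar 1.5 IQR fence starts at the quartiles. Here it starts at the median, which moves the cut-off inward by half an IQR on each side. A rule meant to catch implausible readings then catches the ordinary tails of the distribution.

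This matters because the protocol excludes the flagged values in a sensitivity analysis. Deleting the tails and applying the usual standard error to what remains understates the uncertainty. If one tail is longer than the other, it also moves the mean. An analysis meant to show robustness could then look more precise than the primary one, or disagree with it, because of the rule and not because of bad data.

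**Working it through.** **Inputs.** From Protocol 13.4: SD 17.79, correlation 0.4375, mean change -17.311 mm Hg, 95% confidence, half-width 1 mm Hg with probability 0.9, 1437 pairs, 25% dropout. The documents give no distribution shape and no expected flag rate, so the shapes below are assumptions.

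**The plan's own figure.** SD of the paired difference = 17.79 × √(2 × (1 − 0.4375)) = 18.87. The conditional confidence-interval-width calculation gives 1437 pairs (probability 0.903), and 1437 / 0.75 = 1916. Both are reproduced. The expected full-data half-width is 1.96 × 18.87 / √1437 = 0.98 mm Hg.

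**Flag rate for normal data.** The IQR is 2 × 0.6745 = 1.349 SD.
- 1.5 IQR from the median: 1.5 × 1.349 = 2.02 SD, two-sided tail 4.30%, so 0.0430 × 1437 ≈ 62 patients.
- 1.5 IQR beyond the quartiles: 0.6745 + 2.023 = 2.70 SD, tail 0.70%, about 10 patients.
- Absolute M > 3.5: tail 0.05%, fewer than 1 patient.

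**Interval width for normal data.** With k = 2.0235, φ(k) = 0.0515 and p = 0.0430, the variance of the retained values, relative to the full variance, is 1 − 2kφ(k)/(1 − p) = 1 − 0.2084/0.9570 = 0.782. The SD ratio is √0.782 = 0.884. Allowing for the smaller n, the half-width ratio is √(0.782/0.957) = 0.904, so 0.98 falls to 0.88 mm Hg.

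**Coverage.** In simulation the naive standard error after exclusion is 0.45, while the estimate actually varies with SD about 0.57. The effective multiplier is 1.96 × 0.45/0.57 = 1.55, which corresponds to about 88% coverage.

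**Other shapes.** The fallback is meant for non-normal data, so the normal case is only a reference point. The table gives simulations with n = 1437 and SD 18.87.

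| Assumed shape of the change | Flagged by 1.5 IQR from median | Half-width | Bias (mm Hg) | Coverage | Absolute M > 3.5: flagged, bias, coverage |
|---|---|---|---|---|---|
| Normal | 4.4% | 0.88 | about 0 | 88% | 0.05%, about 0, 95% |
| t, 10 df | 6.2% | 0.82 | about 0 | 88% | 0.5%, about 0, 95% |
| t, 5 df | 8.2% | 0.74 | about 0 | 88% | 1.3%, about 0, 94% |
| Uniform | 0% | 0.98 | about 0 | 96% | 0%, about 0, 96% |
| Skewness -0.25 | 4.4% | 0.88 | +0.87 | 51% | 0.1%, +0.08, 94% |
| Skewness -0.5 | 4.5% | 0.86 | +1.68 | 7% | 0.3%, +0.20, 92% |

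Negative skewness means a longer tail of large falls. Trimming then makes the fall look smaller; positive skewness would do the reverse.

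**Coarse recording.** If normal changes were recorded to the nearest 5 mm Hg, 4.8% would be flagged. At a mean of -17.311 the sample median jumps between -15 and -20, and coverage falls to about 55%. This depends strongly on where the median lies: at a mean of exactly -15 or -20, coverage was about 95%.

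**The case against.** Several points on the other side stand.

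- **Bias does not follow from the flag rate.** A reader might infer that over-flagging makes the estimate biased. For symmetric continuous shapes the bias is about zero. It needs skewness, and the documents give neither its size nor its direction.
- **The 4.3% is for normal data**, for which the protocol prescribes the Z rule. Across the other shapes the rate ran from 0% to about 8%.
- **The switch is not shown to be automatic.** A reader might infer that Shapiro-Wilk would reject almost always at 1437 patients. The protocol names no test; Shapiro-Wilk appears only in the Kazakhstan SAP, where the sample is smaller and nothing is excluded. Selecting patients on baseline pressure truncates the baseline, not the change: in simulated change scores with restricted baseline, rejection was about 4% to 5%. It was 94% for skewness of 0.25 and 100% for 5 mm Hg rounding, but both are assumptions.
- **The primary estimate is largely protected**, since outliers are not removed from it wholesale and actions taken are listed.
- **The threshold printed without an absolute value** might be read as never flagging a very large fall. It is more plausibly a slip of notation.
- **A main-study SAP, if one exists, is not among these documents** and may have settled the matter.

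None of this rescues the rule. Where the fallback applies to near-normal or heavier-tailed data, it gives an interval that is too narrow. The SAP's no-exclusion statement reaches only the Kazakhstan analysis, and there it contradicts the protocol.

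**Conclusion.** The point holds for one analysis: the protocol's outlier-excluded sensitivity analysis when the fallback is used. For near-normal shapes the rule removes about 4% to 5% of genuine values (about 8% for t with 5 df, none for flat data). The naive interval is then about 10% narrower than the full-data interval for near-normal changes, and about 24% narrower for t with 5 df (0.74 against 0.98). Coverage is about 88% in both cases.

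Bias is conditional on skewness: about 0.9 or 1.7 mm Hg at assumed values of -0.25 or -0.5, which is close to or above the 1 mm Hg design half-width.

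The documents do not support a claim that the primary result is distorted, or that the sensitivity estimate must be biased. Separately, they disagree on whether an outlier-excluded analysis is run at all. This is a minor point, worth correcting because the correction is nearly free.

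**What to change.** In Protocol 13.2.5.1 and SAP section 5:

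1. Use absolute M > 3.5 for all variables, with the absolute value printed. Delete the median-based 1.5 IQR fallback and the SAP's Shapiro-Wilk switch.
2. Run the protocol's outlier-excluded sensitivity analysis on that rule.
3. Remove a value from the primary analysis only when a source check confirms an error.
4. Reconcile the protocol's planned exclusion analysis with the SAP's statement that nothing is excluded, and say which applies to the main study and which to the Kazakhstan analysis.

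The cost is a few sentences in each document. Fewer values would be flagged for review: under normality, fewer than 1 instead of about 62 of 1437 per variable. That saves query work, but some moderate recording errors would no longer be picked up by this route and would depend on the ordinary data checks.
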